Prediction: Anodal tDCS targeting VMPFC immediately following extinction learning will improve extinction retention 24 hours later, compared to tDCS during extinction learning and sham stimulation.

Approach: Using a standardized Pavlovian fear conditioning paradigm, 150 participants with a diagnosis of PTSD will be randomized to receive either 1) anodal tDCS targeting the VMPFC during extinction learning, 2) similar tDCS immediately after extinction learning, or 3) sham stimulation. Extinction learning and subsequent extinction retention will be quantified by psychophysiological arousal, i.e. skin conductance responses.

Aim 2: Define temporal tDCS effects on VMPFC activity and psychophysiology during extinction retention.

Prediction: Compared to sham and tDCS during extinction, anodal tDCS after extinction will result in greater VMPFC activation during retention and correlate with associated psychophysiology. Approach:

Participants will undergo fMRI during extinction retention. Imaging analyses will be used to compare groups based on VMPFC activity during extinction retention and its relationship to skin conductance responses.

Exploratory Aim 3: Evaluate whether VMPFC connectivity predicts extinction retention after tDCS.

Prediction: VMPFC to amygdala and hippocampus resting state connectivity will predict extinction retention success, most prominently for participants who received active tDCS after extinction learning.

Approach: Participants will undergo resting state functional connectivity MRI prior to fear conditioning procedures. Imaging analyses will be used to compare groups based on VMPFC to amygdala and hippocampus functional connectivity.

Aim 4 – Sub-study (online): Evaluate the impact of posttraumatic stress symptoms on contextual processing. The objective of this sub-study (“Learning and Memory in Virtual Rooms”) is to test performance differences between configural and elemental contextual processing in individuals across the PTSD spectrum using an online, panel-based platform, e.g., Prolific (<https://www.prolific.co/>).

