Recruitment of 50 participants per group incorporates a conservatively high 15-20% estimate of participants who may not condition while ensuring a sufficient sample size for data analyses.

This study will take place over 4 to 5 visits to Butler Hospital and the MRI Research Facility (MRF) at Brown University. It is possible for baseline procedures to be conducted remotely via phone/HIPAA compliant video conferencing. During these visits, participants will complete informed consent, screening measures, a semi-structured clinical interview, self-report questionnaires, a fear conditioning, extinction, and recall paradigm, and tDCS. Visits will vary in length between 1 to 3 hours.

Any ongoing treatment participants receive will be allowed to continue unchanged throughout the duration of the study, and should be stable for at least 6 weeks prior to start date. Participants will be asked to keep these unchanged during the study period. Treatment changes will be allowed if medically necessary.

The stimuli and experimental protocol to be used in the present study have been used extensively in previous studies examining extinction recall in human populations (19, 57-59). Furthermore, this design has been shown to reliably induce neural and behavioral responses associated with extinction memory (45). In our laboratory, this task has been well-tolerated in individuals with PTSD (53, 54).

C3. Specific Procedures or Treatments

Procedures:

COVID-19 Specific Precautions: Research staff will act in accordance with COVID-19 safety guidelines set by the Brown MRF and Butler Hospital.

Prescreening. Interested individuals will be provided a brief description of the study and prescreened via brief telephone interviews. This prescreening interview will inquire about basic demographic information (e.g. name, age, sex), inclusion and exclusion criteria, and whether they have ever been a patient at Butler Hospital. Inclusion and exclusion criteria may be verified by inspection of the medical record as part of the prescreening process for individuals who have expressed interest in participating (see PHI Waiver below). Those meeting entry criteria will be invited to participate and an appointment date/time will be arranged; additionally, verbal consent for the use of e-mail will be obtained.

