- the Positive and Negative Affect Schedule (PANAS) (66) is a 20-item questionnaire to evaluate general affective status and mood. Ten questions inquire about negative mood states, and the other 10 questions cover positive mood states,
- the State-Trait Anxiety Scale (STAI) (67) to evaluate self-report symptoms of anxiety outside of PTSD symptoms. The STAI contains 20 items for assessing trait anxiety and 20 for state anxiety. State anxiety items include: "I am tense; I am worried" and "I feel calm; I feel secure." Trait anxiety items include: "I worry too much over something that really doesn't matter" and "I am content; I am a steady person." All items are rated on a 4-point scale (e.g., from "Almost Never" to "Almost Always"). Higher scores indicate greater anxiety. Internal consistency coefficients for the scale have ranged from .86 to .95; test-retest reliability coefficients have ranged from .65 to .75

Individuals deemed eligible for the study will be randomized to 1) receiving active tDCS during extinction learning; sham during extinction consolidation, 2) receiving sham during extinction learning; active tDCS during extinction consolidation, 3) receiving sham during extinction learning; sham during extinction consolidation.

Visit Day 2: MRI. Participants may be asked to complete an MRI screening form and a resting state functional MRI scan, described below under MRI in further detail. Expected duration of Visit Day 2 is 1 hour.

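### Exploratory Aim 3 asks whether pre-conditioning connectivity predicts extinction retention, but its only aim-specific analysis compares arms on that connectivity and leaves retention out

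*Combined protocol and SAP*

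**What the plan says.** All the key wording is in section 2.A, Specific Aims.

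- **Aim 3 question:** "Evaluate whether VMPFC connectivity predicts extinction retention after tDCS".
- **Aim 3 prediction:** "VMPFC to amygdala and hippocampus resting state connectivity will predict extinction retention success, most prominently for participants who received active tDCS after extinction learning". This has two parts: an association between connectivity and retention, and a stronger association in one arm.
- **Timing of the scan:** "Participants will undergo resting state functional connectivity MRI prior to fear conditioning procedures". Section C3 places it on Visit Day 2 and makes it optional: "Participants may be asked to complete an MRI screening form and a resting state functional MRI scan". The tDCS is given on Day 4.
- **Analysis for Aim 3:** "Imaging analyses will be used to compare groups based on VMPFC to amygdala and hippocampus functional connectivity".
- **Analysis for Aim 2, for comparison:** "compare groups based on VMPFC activity during extinction retention and its relationship to skin conductance responses".
- **How retention is measured (Aim 1):** "Extinction learning and subsequent extinction retention will be quantified by psychophysiological arousal, i.e. skin conductance responses". The Day 5 text in C3 names the early-recall trials (the first four of each CS+ type) but gives no formula.

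Section C4, Data Analysis, lists linear models, including ANOVA-type, repeated-measures and mixed models, followed by comparisons of stimulation conditions and stimulus types. It does not mention connectivity, a predictor of retention, or a connectivity-by-arm term. The MRI section of C3 covers acquisition only.

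**The concern.** The question is one of prediction, with retention as outcome and connectivity as predictor. The stated analysis has connectivity as outcome and arm as the only explanatory variable. Retention is absent, so the result cannot bear on the question.

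Two things are at stake. A chance imbalance between arms on a pre-stimulation measure could be taken for an Aim 3 result. And the model that does address the aim would be chosen after the data are in, because nothing in the plan fixes it.

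**Working it through.** The documents give no sample size, power or significance level for Aim 3, so there is no planned figure to reproduce. The finding is a comparison of texts; the arithmetic only shows what each analysis can detect.

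**1. What the stated comparison tests.** Connectivity is measured on Day 2, stimulation is given on Day 4, and arms are randomised. The expected difference between arms is therefore zero, whatever the link between connectivity and retention. Retention does not enter the test, so no value of that link can change the rejection rate. At an assumed two-sided 5% level, a simulated one-way ANOVA of connectivity on arm (20,000 runs each) rejected 4.9%, 5.2% and 5.0% of the time at 50, 40 and 25 per arm. This is just the nominal level.

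**2. Side by side with Aim 2.** The two Approach sentences share a template. Aim 2 goes on to name the relationship to skin conductance; Aim 3 stops at connectivity.

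**3. What a model with retention as outcome can show.** Inputs:
- 50 per arm, from C2.
- 40 per arm, assumed. C2 says "Recruitment of 50 participants per group incorporates a conservatively high 15-20% estimate of participants who may not condition", and 50 × 0.80 = 40. C2 does not say that such participants are left out of Aim 3.
- 25 per arm, assumed, because scanning is optional and no number is given.
- Connectivity and retention scaled to SD 1; correlation 0.5 in the after-extinction arm and 0.2 in the other two (assumed).

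Pooled residual variance = [(1 − 0.25) + 2 × (1 − 0.04)] / 3 = (0.75 + 1.92) / 3 = 0.89.

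SE of one arm's slope ≈ √(0.89 / (n − 1)). The difference between the after-extinction slope and the mean of the other two has variance factor 1 + 0.25 + 0.25 = 1.5. The 95% half-width is t × SE on 3n − 6 degrees of freedom.

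- n = 50: SE = √(0.89/49) = 0.135; after-extinction slope ±1.977 × 0.135 = ±0.27; difference ±0.27 × √1.5 = ±0.33.
- n = 25: SE = √(0.89/24) = 0.193; after-extinction slope ±1.995 × 0.193 = ±0.38; difference ±0.38 × √1.5 = ±0.47.

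Simulated median half-widths agree: 0.27 and 0.33 at 50 per arm, 0.39 and 0.48 at 25.

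Simulated power (20,000 runs per cell, two-sided 5%):

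| Correlations (after / others) | Scanned per arm | Overall slope | After-extinction slope | Slope difference |
|---|---|---|---|---|
| 0.5 / 0.2 | 50 | 0.96 | 0.96 | 0.42 |
| 0.5 / 0.2 | 40 | 0.91 | 0.90 | 0.35 |
| 0.5 / 0.2 | 25 | 0.73 | 0.72 | 0.23 |
| 0.3 / 0.3 | 50 | 0.96 | 0.58 | 0.05 |
| 0.3 / 0.3 | 25 | 0.71 | 0.33 | 0.05 |

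Unlike the comparison of arms, this model responds to the association. Its weak point is the slope difference.

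**4. Number of intervals.** Two connections by three slopes give six intervals. With no association at all, at least one excluded zero in 19% to 21% of simulated trials (correlation between the two connectivity measures 0 to 0.6).

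**The case against.** The strongest reply is that this is a loose sentence in an aims summary. It stands directly under a question and a prediction that name predictor, outcome and arm, and comparing groups on connectivity may be shorthand for comparing how connectivity relates to retention in each arm. C4's linear models would accommodate the right regression. The power figures describe a proposed model under assumed correlations; they do not measure harm done by the plan.

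Part of this stands. C4 does not exclude the right model, the figures in the table are illustrative, and the 5% rejection rate is a property of any valid test under randomisation. But C4 does not name the model either, and the Aim 2 sentence shows how the link to outcome is written when it is intended. The sentence as it stands specifies a different analysis from the one the aim needs.

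Three stronger readings are tempting, and the documents support none of them:

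- *Optional scanning biases the arms.* The scan is at the investigator's discretion and follows randomisation, but sessions are double-blind by device code and the scan precedes any stimulation. What can be said is that the number scanned is unknown and the scanned subset may not represent all randomised participants.
- *The investigators will report a baseline difference as the finding.* The wording permits this; nothing shows it is intended.
- *The main result is compromised.* Aim 1 does not use connectivity.

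**Conclusion.** The point holds. The only analysis written for Aim 3 compares randomised arms on a measure taken before stimulation and omits retention, so it tests neither part of the prediction. This follows from scan timing and randomisation and needs no assumed effect size. It is a wrong analysis as worded, beyond a lack of detail, and the general list in C4 does not replace it.

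The consequence is modest: the aim is labelled exploratory, Aim 1 is untouched, and the correction is to wording. The precision and power figures for the replacement rest on assumed correlations, an assumed 5% level, and assumed numbers of 40 and 25 per arm.

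**What to change.** Replace the Aim 3 analysis sentence with:

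> Extinction retention (the Aim 1 skin-conductance measure from the early-recall trials) will be modelled on Day 2 connectivity, arm and connectivity × arm, separately for VMPFC-amygdala and VMPFC-hippocampus connectivity. The overall slope, the after-extinction-arm slope and its difference from the mean slope of the other two arms will be reported with 95% confidence intervals, as exploratory results in the scanned subset, with the number scanned per arm.

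Three points go with it:

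- Write the retention formula once, under Aim 1, and use the same one here.
- C3 makes baseline skin conductance level a covariate but records a baseline before each task phase. If one is used in this model, take one recorded before any Day 4 stimulation, such as the Day 3 pre-conditioning baseline. The Day 5 pre-recall baseline follows tDCS and could be affected by it. The Day 4 one may overlap stimulation, which starts two minutes before extinction learning.
- Keep the comparison of arms on connectivity only as a description of balance.

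Cost: no new visit, scan or participant, but the retention formula has to be settled. The downsides should be stated in the plan. The slope difference is imprecise, so an interval covering zero would be inconclusive. Six intervals are reported without multiplicity control. The scanned subset may not be representative. The contrast with the mean of the other two arms is one reasonable choice; a two-degree-of-freedom interaction test would also address the prediction, provided it is named in advance.

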Taken together, the evidence suggests that finding new ways to increase VMPFC activity – in the framework of extinction – is a promising approach to develop new PTSD treatments. Translational rodent studies support this notion (45, 46). The purpose of the proposed research is to determine whether the timing of transcranial direct current stimulation (tDCS) – a non-invasive brain stimulation technique – targeting the VMPFC affects extinction retention. tDCS alters cortical excitability via subthreshold modulation of neuronal resting membrane potentials using a weak constant electrical current (47, 48). Simplistically said, positive current flow (i.e., anodal stimulation) increases the likelihood of neuronal depolarization, while negative current (i.e., cathodal stimulation) may reduce this likelihood. Hence, tDCS is a truly modulatory technique that does not generate action potentials on its own but works in tandem with ongoing intrinsic neural activation. As such, tDCS biases the brain for subsequent responses to external stimuli to facilitate learning and memory processes (49), including synaptic consolidation.

Prior studies indicate that 1-2mA tDCS can impact fear memory processes (50)(51) and threat vigilance (52) in healthy controls. Yet, clinically more relevant would be to use tDCS in order to improve fear extinction learning and/or consolidation, with the goal to augment extinction retention. Previous work in our lab, indicates this is possible. However, the effects of tDCS appear to depend on the timing of stimulation in relation to extinction learning; whereas tDCS targeting the VMPFC during fear extinction improves subsequent extinction in healthy controls (53), similar tDCS applied during synaptic consolidation may boost extinction memory 24 hours later in Veterans with PTSD (54). These observations on the importance of timing are consistent with the above-mentioned VMPFC-mediated extinction consolidation deficits in PTSD and set the stage for the current study, as it suggests that the

time immediately following extinction learning, i.e. the window of synaptic consolidation, might be a particularly relevant time period for intervention to improve extinction retention in PTSD.

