Prior to starting habituation, participants will individually select electric shock intensity to be "highly annoying but not painful" as the US, following previously used procedures in our lab (53, 54). During habituation participants will be told that the purpose of this phase is to familiarize them with all possible pictures in the experiment, and that no shock would be delivered. Participants will see all stimuli (i.e. to-be CS+E, CS+U, CS-) once in both contexts (CX+ and CX-). After habituation participants will undergo fear conditioning. A total of 32 trials: eight CS+E, eight CS+U, and 16 CS- trials will be presented across two blocks in the CX+ only. Both CS+ trials will be paired with US at a 60% reinforcement rate. The US will occur immediately after CS+ offset. After fear conditioning, participants will complete contingency ratings and the PANAS to assess general affect. Habituation and fear conditioning will either occur at Butler Hospital or in the simulation scanner at the MRF. This visit will last approximately one hour.

Visit Day 4: Extinction of Conditioned Fear. Visit 4 will need to occur 24 hours after visit 3, with an allowable deviation of 4 hours. Extinction learning will either occur at Butler Hospital or in the simulation scanner at the MRF. Participants will be reminded of the instructions and receive either 1) active tDCS during extinction learning, or 2) active tDCS immediately following extinction learning, or 3) sham stimulation according to the randomization schedule. Regardless of randomization group, all participants will be asked to repeat completion of Day 1 tDCS safety screening and tDCS equipment will be placed on the scalp before beginning the task. During the extinction phase a total of 12 trials: six CS+E and six CS- trials will be presented solely in the CX- and no shocks will be delivered. Median split will determine the latter three CS+E trials as 'late extinction' trials. After extinction and tDCS procedures, participants will complete contingency ratings and the PANAS to assess general affect. This visit will last approximately one hour.

Day 5: Extinction Retention and Fear Renewal. Visit 5 will need to occur 24 hours after visit 4, with an allowable deviation of 4 hours. The extinction retention and renewal phases serve as the test phase and

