will either be administered at Butler Hospital or in the real MRI scanner at the Brown MRF. Prior to starting extinction retention, participants will be reminded of the instructions. A total of 32 trials: eight CS+E, eight CS+U, and 16 CS- trials within the CX- only will be presented and no shocks will be delivered. Early recall retention will be based on the first four CS+E and first four CS+U trials. After extinction retention, participants will complete contingency ratings and undergo a fear renewal phase. During fear renewal participants will see the same content as during fear conditioning, but no finger shocks will be delivered. After fear renewal participants will complete contingency ratings and the PANAS to assess general affect. This visit will last approximately one hour.

Skin Conductance. Skin conductance will be recorded for 2 minutes prior to each fear conditioning, extinction and recall phase to establish a physiologic baseline, and continuously throughout each phase. Baseline skin conductance level will be used as a covariate in analysis. To assess skin conductance, two MRI-compatible electrodes will be placed on the thenar eminence of the non-dominant hand, as we will be assessing skin conductance in both the simulator and real scanner depending on task phase as described above. Skin conductance reactivity (SCR) will be quantified by the phasic response that occurs after the presentation onset of each CS+/- stimulus following previous guidelines (57) and our prior work (53, 54). The first trial during fear conditioning will be removed from analyses to avoid the influence of an orienting response on the data. Because of the effects of nicotine and caffeine on SCR we will ask people not to consume nicotine or caffeine two hours prior to the start of the study.

Transcranial direct current stimulation. Device: Continuous direct current stimulation will be delivered by a CE-certified tDCS device (NeuroConn).

tDCS Electrode Montage: We will use a conventional 1 (anode) x 1 (cathode) midline bipolar-non balanced electrode montage (68) with the anode placed approximately over FP1 of the 10-20 EEG coordinate system and the cathode over P10.

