Transcranial direct current stimulation Procedures: Two conductive rubber electrodes will be inserted into reusable sponge pockets saturated with 0.9% normal saline and securely attached to the participant's scalp using a rubber headband prior to beginning the task on Day 4. To reduce the likelihood of side effects, the skin under the stimulation sites will be lightly cleaned with alcohol and inspected for lesions or abnormalities. Participants will be instructed to notify the experimenter of any discomfort. To ensure tDCS tolerability and condition the skin, all participants will receive brief stimulation (1 mA for 30

seconds, with a ramp up/down over 30 seconds each) prior to beginning the task. Impedance, indicating electrode contact quality, will be monitored and recorded throughout tDCS administration. tDCS (or sham) will start 2 minutes prior to extinction learning and will continue throughout the extinction learning phase. For participants randomized to tDCS after extinction learning, tDCS will start immediately after completion of the last extinction trial. We will evaluate tDCS tolerability and adequacy of blinding following task procedures on Day 4. Double-blinding of sessions (active vs. sham) will be achieved through the use of participant-specific blinding codes preset in the tDCS device. [name] (mentor) will generate and oversee unblinded codes. Side effects related to tDCS will be recorded using a tDCS side effects questionnaire, including but not limited to queries about skin discomfort, headache and dizziness based on Brunoni et al. (73), see Appendix.

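### Recorded Day 3 and Day 4 responses have no stated role in the Day 5 comparisons: after versus sham loses precision, and after versus during cannot alone be read as consolidation

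*Combined protocol and SAP*

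**What the plan says.** The Aim 1 prediction (2.A) is: "Anodal tDCS targeting VMPFC immediately following extinction learning will improve extinction retention 24 hours later, compared to tDCS during extinction learning and sham stimulation". Its approach adds: "Extinction learning and subsequent extinction retention will be quantified by psychophysiological arousal, i.e. skin conductance responses".

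The measures are defined in C3. For Day 4: "Median split will determine the latter three CS+E trials as 'late extinction' trials". For Day 5: "Early recall retention will be based on the first four CS+E and first four CS+U trials". No formula combines the two days. The Skin Conductance paragraph of C3 names one covariate, the baseline skin conductance level. C4 lists (M)ANOVA, repeated-measures and mixed models with post-hoc comparisons. It gives no model equation and names no task phase.

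On treatment, C2 gives the after arm and the sham arm the same sham stimulation during extinction learning. In the during arm the current is active at that time; the tDCS procedures in C3 state: "tDCS (or sham) will start 2 minutes prior to extinction learning and will continue throughout the extinction learning phase". In the after arm, active current begins once the last extinction trial is over. The Background (2.B) reports from the group's earlier work that "tDCS targeting the VMPFC during fear extinction improves subsequent extinction in healthy controls".

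**The concern.** Two values that could sharpen or help interpret the Day 5 comparison are collected and then left without a stated use: the Day 3 CS+ response, which precedes stimulation in every arm, and the Day 4 late-extinction response.

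For after versus sham, the contrast that isolates stimulation in the consolidation window, this wastes information. The late-extinction response is a genuine pre-treatment value there, and the contrast could be estimated more tightly at no cost in data.

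For after versus during, the issue is interpretation. The during arm may end Day 4 at a different level of extinction because it learned under current. The CS+U trials do not resolve this. CS+U is never extinguished, so comparing CS+E with it can offset conditioning strength and general arousal, but not how far CS+E was extinguished. A Day 5 difference can therefore come from learning, from consolidation, or from both. At stake is whether the report may attribute it to the consolidation window, on which the Background builds the hypothesis.

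**Working it through.** **Inputs.** The plan gives three arms of 50 (C2), and 3 x 50 = 150 agrees with its total. It states no alpha, power, effect size, SD or correlation, so there is no further figure to reproduce. C2 allows for 15-20% who may not condition; if they are left out, 50 x 0.85 = 42.5 or 50 x 0.80 = 40 per arm remain. Everything else here is assumed: two-sided 5%, normal approximation, SD units, and the correlations and shifts shown.

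**Step 1: what is identical, and until when.** After and sham arms: same Day 3, same sham during Day 4 learning, first difference after the last extinction trial. Late extinction is pre-treatment for this pair. During arm: current starts before the first extinction trial, so late extinction is post-treatment for any contrast that includes this arm. Day 3 is pre-treatment for all three.

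**Step 2: precision, after versus sham.** A pre-treatment covariate with partial correlation r multiplies the standard error by sqrt(1 - r^2).
- r = 0.3: sqrt(1 - 0.09) = 0.954, about 5% smaller.
- r = 0.6: sqrt(1 - 0.36) = 0.80, 20% smaller.

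Without the covariate, the difference detectable with 80% power is (1.96 + 0.84) x sqrt(2/50) = 0.56 SD at 50 per arm, and 0.63 SD at 40. With it, 0.56 becomes 0.56 x 0.954 = 0.53 to 0.56 x 0.80 = 0.45 SD. The relevant r is the partial correlation given CS+U and baseline level, which may already absorb some of this variance.

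**Step 3: after versus during on Day 5, equal consolidation.** Let the during arm end Day 4 lower by d, with a fraction b carried to Day 5. The Day 5 difference is b x d in favour of during.
- d = 0.4, b = 0.5: 0.5 x 0.4 = 0.2 SD. With SE = sqrt(2/50) = 0.2, the chance of significance is Phi(1.00 - 1.96) + Phi(-1.00 - 1.96) = 0.17.
- b from 0.3 to 0.7 and d from 0.2 to 0.8: 0.06 to 0.56 SD, significant 6% to 80% of the time.
- A true 0.5 SD consolidation advantage of after has power Phi(2.5 - 1.96) = 71% with equal learning. With d = 0.4 and b = 0.5 it shows as 0.5 - 0.2 = 0.3 SD, with power Phi(1.5 - 1.96) = 32%.

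If current impairs learning, the signs reverse.

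**Step 4: the Day 4 to Day 5 change in the same case.** During minus after is -0.4 on Day 4 and -0.2 on Day 5, so the difference in change is -0.2 - (-0.4) = +0.2 SD. The during arm appears to lose extinction it did not lose, which favours the study's prediction. In general the offset is (1 - b) x d, opposite in sign to that in Step 3 whenever 0 < b < 1.

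**Step 5: both together.** Let e be the true consolidation advantage of after. Day 5 shows e - b x d and the change shows e + (1 - b) x d, both signed in favour of after. If d > 0, both are positive only when e > b x d. If d < 0, both are positive only when e > (1 - b) x |d|. Under this linear model with b between 0 and 1, agreement in favour of after therefore implies e > 0, in expectation. Neither measure alone gives that.

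**Step 6: covariate adjustment against the during arm.** Besides being post-treatment, late extinction rests on three trials. With b = d = 0.5, measurement reliability of 0.5 to 0.9 leaves 0.25 x (1 - 0.5) = 0.125 down to 0.25 x (1 - 0.9) = 0.025 SD unremoved, even with no unmeasured common cause.

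**The case against.** The strongest reply is that the Day 5 contrast answers the aim as written. The Background defines retention as being able to recall safety memories once extinction has taken place, and treats both learning and consolidation as routes to improving it. Aim 1 asks about timing. If stimulating during learning lowers Day 5 responding, the prediction that after is better has failed, by whatever route. This stands. A reader might infer that the after-versus-during comparison is biased or invalid; the documents do not support that, because arms are randomised and the comparison is a sound total effect.

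A reader might also infer that the plan rules out using Day 4, or knows that the during arm will learn more. Neither follows. C3 gives no exclusive formula, C4 would permit a repeated-measures model across phases, and Day 4 learning is itself to be quantified. The Background sentence concerns subsequent extinction in healthy controls, not Day 4 learning in PTSD. What remains is that the use of these values is not prespecified, and that only one arm learns under current.

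A third tempting step is to let the change score decide whether retention improved. Step 4 shows why not: with carry-over below 1 it errs in the opposite direction, by 0.2 SD in the illustration and towards the prediction.

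Finally, the precision gain is optional and its size uncertain, since CS+U and baseline level may already capture part of it. That also stands.

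**Conclusion.** The point holds as a gap in precision and interpretation, not as a flaw in the randomised comparison. After versus sham is unbiased as planned; adjustment would reduce its standard error by up to about 5-20% if the partial correlation were 0.3-0.6. After versus during is a valid total effect of timing on Day 5 responding, but does not by itself support a statement about consolidation. The part due to learning would be 0.2 SD under the illustrative inputs (0.4 SD, carry-over 0.5) and 0.06-0.56 SD over the wider assumed ranges. The documents supply none of these inputs, so the practical size is unknown. The treatment timing by arm and the absence of a stated role for the Day 3 and Day 4 values rest on the text alone. The change is worth making before analysis, because choosing an adjustment after seeing the data would weaken it.

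**What to change.** Add to C3 and C4:

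1. **After versus sham.** Fit this contrast on those two arms, keep the planned CS+E and CS+U retention measure, and add each participant's Day 4 late-extinction CS+E response as a covariate.
2. **All contrasts.** Include the Day 3 CS+ response as a pre-treatment covariate.
3. **Contrasts with the during arm.** Keep the Day 5 difference as the main result, labelled a total effect of timing, and do not adjust it for late extinction. Report late-extinction response by arm. Give the change from late extinction (last three Day 4 CS+E trials) to early recall (first four Day 5 CS+E trials) as a sensitivity analysis only.
4. **Wording of claims.** Do not make a retention claim depend on the change score. Describe a difference from the during arm as a consolidation effect only if the Day 5 difference and the change agree.

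All values are already recorded. The cost is a little extra analysis and one more measure to report.
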